9.2.1.4 Procedure for Reporting an Adverse Event of Special Interest

For any AESI occurring during the clinical study, regardless of whether or not related to the treatment, the investigator must:

CONFIDENTIAL

1. Take prompt and appropriate medical action, if necessary. The safety of subjects is the first priority.
2. Ensure that the event is evaluated as an AESI. Notify (**within 3 days of receipt of the event**) the Syneos Health Safety and Pharmacovigilance group of an AESI report, by email or fax. Refer to Section 9.2.1.3.

Note: AESI reporting is required by the investigator if it occurs during the clinical study following the first dose of study drug or within 12 weeks (± 5 days) of receiving the last dose of study drug, whether or not the event is considered to be related to the investigational product.

The demographics, medical history, drugs/therapies, and medical and surgical procedures forms must also be available for review in CRF, at that time.

3. Send any relevant information or medical records (eg, laboratory test results) to the Syneos Health Safety and Pharmacovigilance group within 3 days of receipt of this relevant information.
4. Monitor and record the progress of the event until it resolves or reaches a stable condition, with or without sequelae. For all additional follow-up evaluations, update the AESI form within 3 days of receipt of the updated information.
5. Obtain and maintain in the files all pertinent medical records, information, and medical judgments from colleagues who participate in the treatment and follow-up of the subject. If necessary, contact the subject's personal physician or hospital staff to obtain further details.
6. When the outcome of the event is known, update the AESI form, if appropriate.

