9.2.2 Clinical Laboratory Evaluation

The hematology laboratory analyses, clinical chemistry laboratory analyses, and urinalyses will be performed at a central laboratory. Reference ranges will be supplied by the central laboratory and used by the investigator to assess the laboratory data for clinical significance and pathological changes.

The investigator or medically qualified sub-investigator must review and evaluate laboratory values for each subject in a timely manner. Study centers should refer to the current version of the laboratory manual for laboratory values outside of normal limits. For each out-of-range laboratory result, the investigator or designee will evaluate whether he/she considers it to be clinically significant, defined as meeting at least 1 of the following conditions:

- The abnormality suggests a disease and/or organ toxicity, or
- The abnormality is of a degree that requires additional active management, eg, discontinuation of the drug, close observation, more frequent follow-up assessments, or further diagnostic investigation.

If the investigator observes a clinically significant laboratory result, the test will be repeated as soon as possible and the subject will be monitored until the value returns to normal and/or an adequate explanation for the abnormality is found.

Investigators will also be allowed to repeat specific laboratory test(s) or procedure(s) where the investigator suspects an inaccuracy or false result and that which may impact

CONFIDENTIAL

the safety of the subject or the interpretation of the trial results; only after discussion with medical monitor.

All clinically significant out-of-range laboratory values at the screening visit will be recorded in the medical history form (report a diagnosis rather than the laboratory value whenever possible). All clinically significant out-of-range laboratory values after the screening visit are to be reported as an AE if this abnormality was not present at the screening visit or is assessed as having worsened since the screening visit (ie, changed significantly from the screening visit). Whenever possible, the investigator should provide a diagnosis of an AE when reporting the abnormal laboratory value.

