13.1. Adverse Events

Adverse events (AEs) will be coded using MedDRA Version 25.0, March 2022.

Treatment-emergent AEs, defined as those AEs occurring after the first administration of study treatment until end of study, will be tabulated in frequency tables by System Organ Class (SOC) and Preferred Term (PT) based on the Medical Dictionary for Regulatory Activities for each study period (Initial Period, Maintenance Period, and Follow-up Period). Missing date information will be handled using the algorithm described in Section 8.3.

Additional summary tables by SOC and PT will be provided for SAEs, AEs related to the study drug(s), AEs related to the study procedure, adverse events of special interest (AESIs), and AEs leading to treatment discontinuation and study withdrawal.

AEs will be summarized using the number and percent of subjects reporting each SOC and PT and sorted alphabetically by SOC and by descending frequency of PT within SOC.

Subjects who experienced multiple events within the same SOC will be counted once in the SOC summary. When summarizing by causality or maximum severity, if a subject experiences more than 1 occurrence of the same AE, the occurrence with the greatest severity and the closest association with the study drug will be used in summary tables. For summary by maximum severity, subjects who experience multiple occurrence of an AE, the most severe category for each SOC and for each PT within each SOC will be considered in the summary.

TEAEs related to study drug/study procedure are those that are identified as reasonable possibility.

If relationship or severity is missing, the event will be considered as AE related to study drug/study procedure or severe AE.

An AESI is a noteworthy treatment-emergent event for the study drug that should be monitored closely and reported promptly. An AESI can be either serious or non-serious. Based on the potential risks of nemolizumab and the risks associated with biologics in general (i.e., class effects), the following AEs will be considered as AESIs: Injection-related reactions, Newly diagnosed asthma or worsening of asthma, Infections, Peripheral edema:limbs, bilateral, Facial edema and elevated ALT or AST (>3xULN) in combination with elevated Bilirubin (>2xULN).

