13.2. Laboratory Evaluations

13.2.1. Clinical Laboratory Evaluations

The hematology laboratory analyses, clinical chemistry laboratory analyses, and urinalyses will be performed at a central laboratory. Reference ranges will be supplied by the central laboratory and used by the investigator to assess the laboratory data for clinical significance and pathological changes. Reference ranges will be provided in the laboratory manual.

The following parameters will be reported for laboratory data.

- **Hematology:** Hemoglobin, hematocrit, white blood cell (WBC) count (with differential including eosinophils), red blood cell (RBC) count, platelet count, and mean cell volume (MCV).
- **Chemistry:** Creatinine, aspartate aminotransferase (AST), alanine aminotransferase (ALT), gamma glutamyltransferase (GGT), alkaline phosphatase, lactate dehydrogenase (LDH), total bilirubin, direct bilirubin, creatinine phosphokinase ([CPK], CPK isoenzyme test will be performed only if CPK is

This document is confidential.

elevated to $> 2.5 \times \text{ULN}$), albumin, total protein, uric acid, sodium, potassium, calcium, chloride, glucose, urea, total cholesterol, triglycerides, low-density lipoprotein (LDL), and high-density lipoprotein (HDL). Follicle-stimulating hormone (FSH) will be collected for postmenopausal subjects.

- **Urinalysis:** pH, glucose, ketones, blood, protein, leukocytes, nitrites, bilirubin, urobilinogen, and specific gravity.

Laboratory assessments are performed at Screening, Baseline, Week 8, Week 16, Early Termination and Follow-up during the Initial Period.

Laboratory assessments are performed at Week 32, Week 48, Early Termination and Follow-Up during the Maintenance Period.

Hematology and chemistry laboratory data (absolute values and change from Baseline; and change from Week 16 for Maintenance Period) will be summarized as continuous variables (scheduled visits only) for the Initial Period and the Maintenance Period. Urinalysis laboratory data will be summarized by visit (scheduled visit only). Last post-baseline, worst post-baseline and maximum post-baseline results will also be included and will include unscheduled visits in the derivation. And worst post-baseline value will be defined as the highest or lowest value relative to the reference range during the respective treatment Period.

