Shift tables will be generated using the reference ranges (Low, Normal, High and Missing) for hematology and chemistry laboratory data. The number and percentage of subjects shifting from reference ranges between Baseline and each visit (scheduled visits only) will be summarized for the Initial Period and the Maintenance Period. In addition, shift table from Week 16 will be provided for the Maintenance Period. Last, worst and maximum post baseline values will also be included in the shift tables and will include unscheduled visits in the derivation. Worst post baseline value will be defined as the highest or lowest value relative to the reference range.

Summary of the number and percentage of subjects who met criteria of potential clinically significant (CS) value will be summarized (scheduled visits only) for hematology and chemistry laboratory data. Last, worst and maximum post-baseline results will also be included in the summary. Potentially CS ranges for adult and adolescent are listed in sections 22.3 and 22.4.

For statistical and graphical summaries of the laboratory tests, values below or above the limit of detection (e.g. ' < 3 ' or ' > 500 ') are substituted with the lower limit of detection minus 1% for values below the lower limit and are substituted with the upper limit of detection plus 1% for values above the upper limit (e.g. ' < 3 ' is substituted by ' 2.97 ', ' > 500 ' is substituted by ' 505 '). In data listings, the values are shown including the $<$ or $>$ sign.

Distribution of Aspartate Aminotransferase (AST), Alanine Aminotransferase (ALT), Alkaline Phosphatase (ALP), Total bilirubin and Creatinine Phosphokinase (CPK) will be displayed graphically as boxplot by treatment group for each scheduled visit and the maximum post-Baseline (including unscheduled visits in the derivation) values for the Initial Period and the Maintenance Period.

By-subject listing will be presented for all laboratory data. By-subject listing for subjects with at least one abnormal result (out of reference range) will be provided for hematology and clinical chemistry. By-subject listing for subjects with at least one potentially CS result will be provided for hematology and clinical chemistry.

This document is confidential.

All laboratory data will be listed for the Safety population.

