22.3. Potentially clinically significant ranges – Adults

1.0

CD14152.SPR118161.SAP.V01

Approved 10-Nov-2022 00:00:00

Test Parameter	Reference range (as per Lab Manual)		Potentially Clinically Significant Ranges (min and/or max limits)	SI Units
	LLN	ULN		
SERUM				
White Blood Cell Count (WBC)	4.00	10.70	<3.0 at post-baseline and ≥3.0 at baseline >15.0 at post-baseline and ≤15 at baseline	x10E9/L
Neutrophils (absolute)	1.60	7.40	<1.5 at post-baseline and ≥1.5 at baseline >9 at post-baseline and ≤9 at baseline	x10E9/L
Eosinophils (absolute)	0.00	0.70	>0.7 at post-baseline and ≤0.7 at baseline	x10E9/L
Basophils (absolute)	0.00	0.20	>0.2 at post-baseline and ≤0.2 at baseline	x10E9/L
Monocytes (absolute)	0.10	0.90	>0.9 at post-baseline and ≤0.9 at baseline	x10E9/L
Lymphocytes (absolute)	1.00	4.00	<0.8 at post-baseline and ≥ 0.8 at baseline >4.0 at post-baseline and ≤ 4.0 at baseline	x10E9/L
Hemoglobin *Male **Female	* 135.00 ** 120.00	* 175.00 ** 160.00	* <100 g/L at post-baseline and ≥ 100 g/L at baseline * ≥200 g/L at post-baseline and < 200 g/L at baseline ** <90 g/L at post-baseline and ≥ 90 g/L at baseline ** ≥180 g/L at post-baseline and < 180 g/L at baseline	g/L
Hematocrit *Male **Female	* 0.40 ** 0.36	* 0.52 ** 0.46	<0.30 at post-baseline and ≥ 0.30 at baseline >0.6 at post-baseline and ≤ 0.6 at baseline	L/L
Platelets	150.00	350.00	<100 at post-baseline and ≥ 100 at baseline >700 at post-baseline and ≤ 700 at baseline	x10E9/L
Sodium	135.00	148.00	<129 at post-baseline and ≥ 129 at baseline >150 at post-baseline and ≤ 150 at baseline	mmol/L
Potassium	3.50	5.30	<3.5 at post-baseline and ≥ 3.5 at baseline >5.5 at post-baseline and ≤ 5.5 at baseline	mmol/L
Calcium - total	2.14	2.62	<2 at post-baseline and ≥ 2 at baseline	mmol/L
Chloride	98.00	110.00	<95 at post-baseline and ≥ 95 at baseline >115 at post-baseline and ≤ 115 at baseline	mmol/L
Glucose	3.90	6.90	<3 at post-baseline and ≥ 3 at baseline >13.9 at post-baseline and ≤ 13.9 at baseline	mmol/L
Creatinine *Male **Female	* 62 ** 44	* 106 ** 80	>1.5 x ULN at post-baseline and ≤1.5 x ULN at baseline	µmol/L
Blood urea nitrogen (BUN)	2.1	8.9	>8.9 at post-baseline and ≤8.9 at baseline	mmol/L
AST	0.00	41.00	>3 x ULN at post-baseline and ≤3 x ULN at baseline	U/L
ALT	0.00	45.00	>3 x ULN at post-baseline and ≤3 x ULN at baseline	U/L
Alkaline phosphatase *Male **Female	* 40 ** 35	* 129 ** 104	>2.5 x ULN at post-baseline and ≤2.5 x ULN at baseline	U/L

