Bilirubin total	0.00	21.00	>1.5 x ULN at post-baseline and ≤1.5 x ULN at baseline	µmol/L

This document is confidential.

1.0

CD14152.SPR118161.SAP.V01

CPK				
*Male	20.00	* 200	>2.5 x ULN at post-baseline and ≤2.5 x ULN at baseline	U/L
**Female		** 180	>2.5 x ULN at post-baseline and ≤2.5 x ULN at baseline	
GGT	0.00	65.00	>2.5 x ULN at post-baseline and ≤2.5 x ULN at baseline	U/L
Protein total	60.00	85.00	<50 at post-baseline and ≥50 at baseline >95 at post-baseline and ≤95 at baseline	g/L
Albumin	32.00	55.00	<30 at post-baseline and ≥30 at baseline	g/L
Uric acid	* 0.24	* 0.51	* >0.51 at post-baseline and ≤0.51 at baseline	mmol/L
*Male				
**Female	** 0.15	** 0.45	** >0.45 at post-baseline and ≤0.45 at baseline	
Cholesterol total	0.00	5.17	>7.75 at post-baseline and ≤7.75 at baseline	mmol/L
Triglycerides	0.00	2.25	>3.42 at post-baseline and ≤3.42 at baseline	mmol/L
VITAL SIGNS and WEIGHT				
Pulse rate	N/A	N/A	≤50 bpm and decrease from baseline ≥20 bpm ≥120 bpm and increase from baseline ≥20 bpm	beats/min
Diastolic blood pressure	N/A	N/A	≤45 mmHg and decrease from baseline ≥10 mmHg ≥110 mmHg and increase from baseline ≥10 mmHg	mmHg
Systolic blood pressure	N/A	N/A	≤95 mmHg and decrease from baseline ≥20 mmHg ≥160 mmHg and increase from baseline ≥20 mmHg	mmHg
Weight	N/A	N/A	≥5% increase from baseline ≥5% decrease from baseline	

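### The hepatic AESI is a laboratory rule, but no planned table counts the subjects whose values meet it and no reconciliation with reported events is planned

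*SAP*

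**What the plan says.** **Definition.** SAP 13.1 lists among the AESIs "elevated ALT or AST (>3xULN) in combination with elevated Bilirubin (>2xULN", as do Protocol 6.3 and 9.2.1.1. Neither document says whether the two elevations must come from the same draw, or whether bilirubin means total or direct (Protocol 9.2.2.2 measures both).

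**How a case enters the AESI tables.** Protocol 9.2.1.4 instructs the investigator: "Ensure that the event is evaluated as an AESI". It adds that "AESI reporting is required by the investigator if it occurs during the clinical study following the first dose of study drug". For laboratory results in general, Protocol 9.2.2 says: "For each out-of-range laboratory result, the investigator or designee will evaluate whether he/she considers it to be clinically significant". SAP 13.1 then tabulates AESIs as treatment-emergent adverse events by category, SOC and PT.

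**What is done with the laboratory values.** SAP 13.2.1 states that hematology and chemistry analyses and "urinalyses will be performed at a central laboratory". It plans continuous summaries, low/normal/high shift tables, single-analyte box plots, by-subject listings and PCS counts: "Summary of the number and percentage of subjects who met criteria of potential clinically significant (CS) value will be summarized". In SAP 22.3 the adult AST and ALT rows each read ">3 x ULN at post-baseline and ≤3 x ULN at baseline", and the total bilirubin row reads ">1.5 x ULN at post-baseline and ≤1.5 x ULN at baseline". SAP 22.4 has the same form for adolescents, with different ALT limits.

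**The concern.** The criterion is fully measurable from results that will sit in the database, yet the only planned count of it depends on an adverse-event record. A subject whose values meet the rule, but for whom no event was entered, would be missing from every AESI table. The laboratory tables do not fill the gap, because none links transaminases and bilirubin within a subject.

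The stake is the completeness of the hepatic safety statement by arm. A count of zero or near zero is informative only if ascertainment is complete.

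The SAP treats the respiratory signal differently. Protocol 9.2.1.1 also makes a PEF below 80% of predicted reportable as an AESI in subjects with a history of asthma. For that signal, SAP 13.6.1 and 13.6.2 count PEF below 80% and ACT of 19 or less directly from the measurements. Asthma events are also adjudicated, and investigator reports are tabulated against the committee's outcome. The hepatic AESI, equally numeric, has neither a derived count nor a stated cross-check.

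**Working it through.** The plan states no figure on this point, so there is none to reproduce. Three checks were made.

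**1. The rule in laboratory units** (ULNs from SAP 22.3 and 22.4)

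- Adults: ALT 3 x 45 = 135 U/L; AST 3 x 41 = 123 U/L; bilirubin 2 x 21 = 42 µmol/L.
- Adolescents: ALT 3 x 30 = 90 U/L (male) or 3 x 20 = 60 U/L (female); AST 3 x 41 = 123 U/L; bilirubin 2 x 21 = 42 µmol/L.
- PCS bilirubin cut, both age groups: 1.5 x 21 = 31.5 µmol/L.

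**2. Can the PCS flags reproduce the rule?** Work in multiples of ULN.

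- AESI rule: post-baseline transaminase > 3 and post-baseline bilirubin > 2.
- Both PCS flags: (post-baseline transaminase > 3 and baseline ≤ 3) and (post-baseline bilirubin > 1.5 and baseline ≤ 1.5).

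A grid of nine multiples from 0.5 to 4.0, for baseline and post-baseline of one transaminase and bilirubin, gives 9^4 = 6,561 combinations:

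- 648 meet the AESI rule. Of these, 168 carry both flags and 480 do not. Every one of the 480 has baseline transaminase > 3 or baseline bilirubin > 1.5.
- 84 carry both flags without meeting the rule. All have post-baseline bilirubin between 1.5 and 2.

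These are logical combinations, not patient frequencies. They show that mismatches are of two kinds only: cases dropped by the baseline condition, and extra subjects in the 1.5 to 2 band.

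The published rows are weaker still, because they are separate totals. If *a* subjects are in a transaminase row and *b* in the bilirubin row out of *N*, the number in both can lie anywhere from max(0, a + b − N) to min(a, b). Worst and maximum values are also taken analyte by analyte, so they may come from different visits.

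**3. Is a joint output planned elsewhere?** The chemistry outputs in the SAP indexes run from 14.3.4.1.2.1 to 14.3.4.1.2.19 with no gap (tables and listings .1 to .9, figures .10 to .19), so redaction does not explain the absence. None combines the analytes. Listings 14.3.4.1.2.8 (abnormal chemistry), 14.3.4.1.2.9 (PCS chemistry) and 16.2.8.1.2 (all chemistry) are by subject and would show both analytes, but they give no count.

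**Illustration of size.** With 750 subjects randomized 2:1, nemolizumab has 750 x 2/3 = 500. For zero reported cases, the one-sided 95% upper bound is 1 − 0.05^(1/500) = 0.60%. If a fraction *s* of true cases is reported, the bound on the true rate is that figure divided by *s*. The values of *s* are assumptions; the documents give none.

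| Assumed *s* | Upper bound |
|---|---|
| 100% | 0.60% |
| 90% | 0.66% |
| 75% | 0.80% |
| 50% | 1.19% |

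**The case against.** The strongest reply is that the cases are visible and that reporting is not optional. The abnormal-results and full chemistry listings have no baseline condition. ALT, AST and bilirubin belong to one panel, and listings are sorted by subject and collection day, so a medical reader could find every joint elevation. Protocol 9.2.1.1 states the hepatic rule without the clinical-judgment wording attached to several asthma items. Protocol 9.2.1.4 requires AESI reporting whether or not the event is thought related, and the IDMC monitors AESIs. Laboratory alerts or a laboratory-to-AESI check may exist in the laboratory manual, the data management plan or the IDMC charter, none of which is available here. The documents also do not present liver injury as a leading risk: Protocol 6.2.3 names asthma and infections as the potential important risks.

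Most of this stands, and it rules out several stronger readings:

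- **That the 1.5 x ULN bilirubin cut is a defect.** Any value above 2 x ULN is also above 1.5 x ULN, so the lower cut loses no case. Nothing requires a general PCS grid to match AESI thresholds.
- **That a subject with a high baseline transaminase goes unseen.** Such a subject escapes only the PCS flag. The listings, shift tables and maximum post-baseline summaries still show the values. A baseline condition is also reasonable for a grid meant to show new crossings.
- **That the hepatic conclusion rests on site vigilance alone.** The values are listed; what is missing is a planned count and comparison.
- **That only events flagged by the investigator as AESIs are tabulated.** SAP 13.1 does not say how the category is assigned. What the tables do need is a recorded adverse event.

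The reply leaves the main point untouched. A listing does not yield a count by arm, and the SAP does not commit anyone to searching it or to comparing the result with the reported AESIs. Alerts in other documents would help sites recognise cases but would not supply a planned analysis.

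**Conclusion.** The point holds as a gap in the planned outputs. An AESI defined by laboratory values is counted only through recorded events, no table gives the number of subjects per arm who meet the joint criterion, and no reconciliation is stated. The PCS rows cannot stand in, because they do not link the two elevations within a subject and they leave out subjects above a cut at baseline.

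It is a cheap improvement. The documents give no evidence that cases will be missed, and no rate from which to estimate how many. The bounds above depend wholly on assumed reporting fractions. The conclusion also assumes that the SAP indexes list every planned chemistry output, and it makes no claim about checks in documents not seen.

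**What to change.** In SAP 13.2.1, add one derived table and one listing, by period and arm, of subjects with ALT or AST above 3 x ULN and total bilirubin above 2 x ULN after first dose.

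- **Timing:** the primary row uses the same draw. A second row uses a wider window, fixed in the SAP before unblinding.
- **Data:** include unscheduled samples and any local results obtained under Protocol Appendix 2, each judged against the ULN of the laboratory that ran it.
- **Baseline:** do not exclude on baseline. Show baseline ALT, AST and bilirubin status in the listing so that cases that are not treatment-emergent can be identified.
- **Reconciliation:** compare derived cases with reported hepatic AESIs before database lock, query mismatches, and report any that remain.

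No change to the PCS cuts in SAP 22.3 or 22.4 is needed.

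The cost is one derived flag, one extra table with its listing, and a reconciliation step before lock. No new data are collected.
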